6. SUBJECT RECRUITMENT & SCREENING

Based on the results from Cotton et al, median transfusion in the component therapy group was 6 PRBC in the first 24 hours and 4 PRBC equivalents in the whole blood group. The standard deviation (estimated from the interquartile range) was approximately 4. Thus with an expectation of alpha = 0.05 and expected power of 90% to detect a similar 2 unit difference in transfusion volume, a sample size of 190 should be sufficient; thus our projected sample size of 200 should be more than adequate. Age range will be 18 years and older, and only males will be included in the study. Our expected racial/ethnic distribution will be approximately 60% white, 15% black, 8% Asian, and 18% other race. No actual recruitment will be performed; rather all qualifying patients will be included. Consent waiver is being requested.

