8. STUDY DESIGN

a. Background or rationale for this study.

Whole blood transfusion was used in World War I, World War II, Korea and Vietnam. By the end of the Vietnam conflict, whole blood had been separated into components for ease of use and more focused transfusion. As a result, transfusion practices did not catch up with the available units. More recent investigations have revealed that patients have fewer deaths from hemorrhage when the ratios of FFP:RBC units and platelet:RBC units approaches 1:1. Furthermore, the success of “walking blood banks” with fresh whole blood transfusion in the 2nd Iraq war and the war in Afghanistan have prompted new interest in the civilian use of whole blood. While civilian centers cannot use walking blood banks as we do not have a pre-screened population from which to draw, low-titer type O positive whole blood (LTOWB) can be used. One LTOWB unit is equivalent to one unit of PRBC and one unit of FFP. While LTOWB has been studied, the inclusion criteria for past studies has been less inclusive than in this trial, specifically excluding patients with severe traumatic brain injuries even if they also had exsanguinating hemorrhage. Furthermore, at Loma Linda University Medical Center we will have the opportunity to randomize patients to receive whole blood as their first transfusion, thus maximizing the potential benefits. Finally, we have the opportunity to study the coagulopathy associated with these patients by using viscoelastic testing.

b. Objectives

1. Evaluate PRBC equivalents transfused in each group in the first 24 hours (Primary outcome)
2. Evaluate total transfusion in each group in the first 24 hours (Secondary Outcome) including breakdown by FFP equivalents, platelet units, and cryoprecipitate
3. Evaluate 6 hour, 24 hour, and hospital mortality (Secondary Outcome)
4. Evaluate ICU outcomes in each group:
 1. ICU length of stay

- 2. Ventilator days
- 3. SOFA score on day of ICU discharge
- 4. Presence of ARDS?
- 5. Presence of TRALI?
- 6. Presence of DVT/PE?
- 7. Necessity for Dialysis?
- 8. Necessity for Tracheostomy?
- 5. Evaluate viscoelastic testing parameters in both groups when sent on arrival in ICU
 - 1. Percentage of patients with EXTEM clotting time > 80 sec
 - 2. Percentage of patients with EXTEM amplitude at 10 min < 40mm and FIBTEM amplitude at 10 min \leq 10mm
 - 3. Percentage of patients with EXTEM amplitude at 10 min < 40mm and FIBTEM amplitude at 10 min > 10mm

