 - 4. Percentage of patients with maximum thrombolysis > 15%
- 6. Interval analyses to be performed after 6 and 12 months with provision to continue the study out to 24 months.
 - 1. Stopping rule: A statistically significant difference in hospital mortality at 6 months or 12 months
 - 1. If in favor of LTOWB, consideration of trial termination and making LTOWB the primary standard of care for all trauma patients receiving emergency transfusion except for child-bearing age females (unless Rh immunoglobulin can be administered)
 - 2. If in favor of component therapy, consideration of trial termination and making component therapy the primary standard care for all trauma patients receiving emergency transfusion
- c. Procedures involved (Research Interventions)

*Chronological order of all research interventions, **distinguishing standard of care vs. research intervention.***

- 1. Level A trauma paged out with gender of patient
- 2. For female patients, care proceeds as normal
 - 1. Standard trauma cooler containing 4 units O- PRBC and 4 units FFP dispatched to trauma bay (if overall supply is short the first cooler may contain 2 units O- PRBC and 2 units FFP)
 - 2. Transfusion proceeds per trauma and ED team
 - 3. Patient data not included in the study

3. For male patients, the blood bank will randomize patients to the LTOWB group or the CT (component therapy) group based on a prespecified calendar-based randomization scheme by week:
 1. LTOWB: Cooler containing 2 or 4 units of LTOWB dispatched to trauma bay depending on supply
 2. CT: Standard trauma cooler containing 4 units O+ PRBC and 4 units FFP dispatched to trauma bay (if overall supply is short the first cooler may contain 2 units O+ PRBC and 2 units FFP)
 3. Transfusion proceeds per trauma and ED team
 4. Blood work (CBC, BMP, tox screen, ROTEM viscoelastic test, PT/INR, PTT, venous lactate) sent as per standard of care for all patients.
 5. Hemorrhage control and other diagnostic evaluations performed in all patients per standard of care.
 6. Patients arrive in ICU and have additional blood work (CBC, CMP, possibly ABG, ROTEM viscoelastic test, PT/INR, PTT, venous lactate, possibly fibrinogen) sent per standard of care by the ICU team.
 7. Clinical data on survival and transfusion monitored
- d. Alternative procedures, if any, that are not included in the study but might be advantageous to the subject. N/A

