University of Texas at Houston, patients were blood typed prior to inclusion in the study. Furthermore, all type B and AB patients were excluded, as were patients with significant traumatic brain injury or if they received more than 4 units of blood prior to randomization. Patients were also excluded if they could not, in the judgment of the attending surgeon, wait for blood typing. Thus, out of 357 patients who could have met criteria for inclusion, only 107 were actually randomized, introducing selection bias. In particular, the exclusion for the patients felt to be “too sick to wait” for blood typing may have excluded some sicker patients who would have benefited from whole blood. However, this study did demonstrate a reduction in transfusion volumes for patients after those with brain injury were excluded. (5)

As can be seen, the current field of literature leaves multiple unanswered questions that will be answered by the proposed study.

- 1) Does transfusion with low-titer O-positive whole blood reduce the amount of transfusion within 24 hours of arrival?
- 2) Does transfusion with low-titer O-positive whole blood reduce 6 hour, 24 hour, or hospital mortality?
- 3) What is the effect of low-titer O-positive whole blood transfusion on coagulopathy after trauma, as demonstrated by viscoelastic testing?
- 4) Is the potential benefit of transfusion with low-titer O-positive whole blood restricted only to patients receiving massive transfusion (6 units PRBC or more) or in all patients receiving emergency transfusion?
 - g. If an Investigational New Drug (IND) is involved, provide the following information: (1) name of drug, (2) source of drug, (3) dosage and schedule of administration, (4) status with Food and Drug Administration and IND#, (5) review of animal studies and previous human studies, (6) reported side effects

N/A

- h. For an approved drug used in an experiment, provide similar information: (1) name, (2) source, (3) dosage, (4) how administered, (5) side effects.

N/A

- i. If an Investigational Device (ID) is involved, provide the following information: (1) name of device, (2) manufacturer, (3) status with Food and Drug Administration and ID#, (4) review of animal studies and previous human studies, (5) reported adverse effects.

N/A

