9. DATA COLLECTION

Data collection procedures: to include lab evals, tests, specimen amounts and schedules, clinical assessments/schedule/follow up procedures, case report forms, data collection forms (with description of subject codes), study instruments, rating scales, interview guides.

RedCap Database to be created with the following data

Age (years)

Penetrating Trauma (0=no, 1=yes)

Penetrating Mechanism (1=stab, 2=gsw, 3=impalement, 9=other)

Blunt Mechanism (1=MVC, 2=Fall, 3=MCC, 4=ped vs auto, 5=assault, 9=other)

Scene transport (0=no, 1=yes)

Injury Severity Score (1-75)

Abbreviated Injury Score-Head (0-6)

Predominant site of hemorrhage (1=upper extremity, 2=lower extremity, 3=axilla, 4=groin, 5=head/neck, 6=chest, 7=abdomen, 8=pelvis, 9=other)

Tourniquet in Place (0=no, 1=yes)

Pre-LLUMC PRBC (# units)

Pre-LLUMC FFP (# units)

Pre-LLUMC PLT (# unitss

Pre-LLUMC Cryo (# units)

Pre-LLUMC Crystallloid (# liters)

Pre-LLUMC Cardiac Arrest? (0=no, 1=yes with ROSC, 2=yes without ROSC)

Arrival SBP (0 = in arrest)

Arrival HR (0 = in arrest)

Arrival Temperature (Celsius)

Arrival O2 saturation (0 = in arrest)

Arrival GCS (3-15)

Treatment Group (0 = Component Therapy, 1 = LTO+WB)

LLUMC ED WB (# units)

LLUMC ED PRBC (# units)

LLUMC ED FFP (# units)

LLUMC ED PLT (# unitss

LLUMC ED Cryo (# units)

LLUMC ED Crystallloid (# liters)

LLUMC ED Cardiac Arrest? (0=no, 1=yes with ROSC, 2=yes without ROSC)

LLUMC ED Thoracotomy (0=no, 1=yes)

LLUMC ED Laparotomy (0=no, 1=yes)

LLUMC ED Death? (0=no, 1=yes)

LLUMC ED ABG results

pH

Hgb

Lactate

LLUMC ED Hgb from CBC

LLUMC ED PLT count from CBC

LLUMC ED INR

LLUMC ED PTT

LLUMC ED Fibrinogen

LLUMC ED ROTEM results

EXTEM CT

EXTEM A10

If EXTEM A10 < 40mm, FIBTEM A10

EXTEM ML

Hemorrhage Control Environment (HCE) (0=none, patient died in ED, 1=none, patient direct to ICU, 2=OR, 3=IR, 4=OR and IR, 5=Hybrid OR)

LLUMC HCE WB (# units)

LLUMC HCE PRBC (# units)

LLUMC HCE FFP (# units)

LLUMC HCE PLT (# unitss

LLUMC HCE Cryo (# units)

LLUMC HCE Crystalloid (# liters)

LLUMC HCE Cardiac Arrest? (0=no, 1=yes with ROSC, 2=yes without ROSC)

LLUMC HCE Thoracotomy (0=no, 1=yes)

LLUMC HCE Laparotomy (0=no, 1=yes)

LLUMC HCE Pelvic Packing (0=no, 1=yes)

LLUMC HCE Neck Exploration (0=no, 1=yes)

LLUMC HCE Exploration for Axilla/Upper Extremity (0=no, 1=yes)

LLUMC HCE Exploration for Groin/Lower Extremity (0=no, 1=yes)

LLUMC HCE Death? (0=no, 1=yes)

LLUMC HCE ABG results #1 (first in HCE)

pH

Hgb

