
Lactate

LLUMC HCE ABG results #2 (last in HCE)

pH

Hgb

Lactate

LLUMC HCE ROTEM results #1 (first in HCE, if sent)

EXTEM CT

EXTEM A10

If EXTEM A10 < 40mm, FIBTEM A10

EXTEM ML

LLUMC HCE ROTEM results #2 (last in HCE, if sent)

EXTEM CT

EXTEM A10

If EXTEM A10 < 40mm, FIBTEM A10

EXTEM ML

LLUMC ICU/Floor Transfusion within first 24 hours (not including blood given prior to LLUMC, in LLUMC ED, and in LLUMC HCE)

LLUMC ICU WB (# units)

LLUMC ICU PRBC (# units)

LLUMC ICU FFP (# units)

LLUMC ICU PLT (# unitss

LLUMC ICU Cryo (# units)

LLUMC ICU Crystalloid (# liters)

LLUMC ICU ABG results

pH

Hgb

Lactate

LLUMC ICU Hgb from CBC

LLUMC ICU PLT count from CBC

LLUMC ICU INR

LLUMC ICU PTT

LLUMC ICU Fibrinogen

LLUMC ICU ROTEM results

EXTEM CT

EXTEM A10

If EXTEM A10 < 40mm, FIBTEM A10

EXTEM ML

Clinical Endpoints

Patient Dead on Arrival (0=no, 1=yes)

Patient Died within 6 hours of arrival (0=no, 1=yes)

Patient Died within 24 hours of arrival (0=no, 1=yes)

Patient Died Prior to Discharge (0=no, 1=yes)

Duration of Mechanical Ventilation (Days)

Duration of ICU Stay (Days)

Duration of Hospital Stay (Days)

Presence of ARDS?

Presence of TRALI?

Presence of DVT/PE?

SOFA Score on Day of ICU Discharge

Need for Dialysis During Hospitalization (0=no, 1=yes)

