11. DATA ANALYSIS

Analysis to be performed by median/IQR with nonparametric comparison of medians for central tendency. P value of 0.05 indicates statistical significance. Patients with death on arrival will be excluded from data reporting as they are a different patient population. Intentional sub-analysis will be performed on patients who received less than 6 units PRBC or equivalent in the first 4 hours or 6 units and more PRBC in the first 4 hours (massive transfusion). Also, an intentional sub-analysis will be performed on the patients who were classified as dead on arrival. Separate sub-analyses will be performed on patients with Abbreviated Injury Score (Head) of 3 or greater indicating severe traumatic brain injury.

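### The massive-transfusion split uses units received in the first 4 hours, a count that treatment can change and that is part of the primary outcome, so it cannot show who benefits from LTOWB

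*Combined protocol and SAP*

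**What the plan says.** Section 8.f, question 4, asks whether any benefit is "restricted only to patients receiving massive transfusion (6 units PRBC or more) or in all patients receiving emergency transfusion". Section 11 plans a sub-analysis of "patients who received less than 6 units PRBC or equivalent in the first 4 hours or 6 units and more PRBC", both counted over 4 hours, and calls the upper group massive transfusion. No other planned analysis uses that threshold or term. Section 11 gives no interaction test, no baseline definition of massive-transfusion risk and no caution about reading the split.

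Section 8.b sets the primary objective: "Evaluate PRBC equivalents transfused in each group in the first 24 hours (Primary outcome").

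On timing, section 8.a says the trial can "randomize patients to receive whole blood as their first transfusion". Section 8.c has the blood bank assign the arm and then send the product, in the LTOWB arm a "Cooler containing 2 or 4 units of LTOWB dispatched to trauma bay depending on supply".

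Section 6 takes its planning values from a cited pilot randomised trial: "median transfusion in the component therapy group was 6 PRBC in the first 24 hours and 4 PRBC equivalents in the whole blood group", with an SD of about 4.

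Section 9 records units by location, for example "LLUMC ED PRBC (# units") and "LLUMC ICU/Floor Transfusion within first 24 hours". It lists no 4-hour count.

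**The concern.** A subgroup comparison keeps the protection of randomisation when the subgroup is fixed before treatment. Here membership depends on how much blood the patient received after the assigned product was sent, and reduced transfusion is the effect the trial is looking for. If LTOWB changes who reaches 6 units in 4 hours, the patients with 6 or more units in one arm are not the counterparts of those in the other, and the same holds under 6. The grouping variable is also a component of the outcome compared within the groups.

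Question 4 is one of four named study questions. At stake is a report that benefit is limited to, or absent from, massive transfusion when the pattern comes from the grouping.

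**Working it through.** The plan gives no figure for this sub-analysis, so there is nothing to reproduce first.

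**Inputs from the documents.** Cut at 6 units in 4 hours (section 11); 24-hour medians of 6 and 4, SD about 4 estimated from an IQR, 200 patients (section 6). The planning CT median equals the cut, but the median is for 24 hours and the cut is for 4.

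**Assumptions.** 100 patients per arm. Three distributions for CT units, rounded, minimum 1:
- lognormal, median 6, log-SD 0.646, chosen so that the IQR is 6 × (1.546 - 0.647) = 5.4 = 1.35 × 4
- negative binomial, mean 6.5, SD 4
- normal (6, 4) truncated at 0.5

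**Target.** The plan states none. I use the effect in patients classified by the 4-hour units they would need under CT. For stratum s, with Y the 24-hour units and U the 4-hour units:
- True(s) = mean of (Y under LTOWB - Y under CT) among patients whose U under CT is in s
- Observed(s) = mean Y of LTOWB patients with received U in s, minus mean Y of CT patients with received U in s

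Negative values favour LTOWB.

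**Step 1: who crosses the cut.** Suppose all units are given within 4 hours.
- Saving 2 units: 6 - 2 = 4, 7 - 2 = 5, 8 - 2 = 6. Patients needing 6 or 7 units leave the upper stratum in the LTOWB arm only. LTOWB's upper stratum then starts at a need of 8 while CT's starts at 6, and LTOWB's lower stratum reaches a need of 7 while CT's stops at 5.
- Saving one third: 8 × 2/3 = 5.3, rounded to 5; 9 × 2/3 = 6. Patients needing 6, 7 or 8 units cross.
- Saving 3 units only from a need of 9 upward: 9 - 3 = 6. Nobody crosses.

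**Step 2: size of the bias.** All units within 4 hours, 1,000,000 simulated patients per arm, ranges over the three distributions:

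| Effect of LTOWB | 6 or more: true | observed | Under 6: true | observed |
|---|---|---|---|---|
| Every patient saves 2 units | -2.0 | +0.1 to -0.7 | -1.6 to -1.8 | -0.6 to -1.0 |
| Every patient saves one third | -2.9 to -3.5 | -1.4 to -1.6 | -1.1 to -1.2 | -0.1 to -0.4 |
| Only needs of 9 or more save 3 units | -1.5 to -1.6 | as true | 0 | 0 |
| A random 30% stop at 2 units | -2.1 to -2.5 | 0.0 | -0.42 to -0.49 | -0.64 to -0.78 |

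In the first two rows both strata understate the benefit. With the 2-unit saving, 54-60% of CT and 34-39% of LTOWB patients reach 6 units. In the third row there is no bias, although mean 4-hour units fall by 0.8-0.9. In the fourth, the two strata are biased in opposite directions: against LTOWB at 6 or more, for it under 6.

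**Step 3: timing.** For the two uniform savings, let recovery = Observed / True.

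| When units are saved | Scenarios | CT reaching 6 | LTOWB reaching 6 | Recovery, 6 or more | Recovery, under 6 |
|---|---|---|---|---|---|
| Spread over 24 hours (4-hour share 60-100%) | 18 | 24-60% | 7-39% | -10% to 61% | 7% to 75% |
| From the first 4 hours (share 60-80%) | 12 | 24-45% | 2-25% | -66% to 52% | 22% to 60% |
| Only after 4 hours (share 60-80%) | 12 | 24-45% | 24-45% | 100% | 100% |

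**Step 4: what a trial of 100 per arm would show** (two-sided Wilcoxon test, 2,000 trials, significant in favour of LTOWB):
- Lognormal, 2-unit saving spread over 24 hours, 80% of units in 4 hours: 2% at 6 or more, 97% under 6.
- Truncated normal, one-third saving, all units in 4 hours: 87% at 6 or more, 4% under 6.

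In both the saving is uniform, yet it would usually be seen in one stratum only, and in a different one each time.

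**The case against.** The strongest objection concerns direction. A reader might infer that any early saving biases both strata against LTOWB. The documents do not support that: they give no effect shape, and question 4 itself asks whether the effect is uneven. The last two rows of the first table show an early saving with no bias, and one where the under-6 comparison favours LTOWB. Early deaths add to this. Only patients dead on arrival are excluded, so deaths within 4 hours stay in with truncated counts, and section 13 names survival benefit as possible. In one illustration (about 15% early deaths, 40% averted, need lowered by 0.5 units) the under-6 bias favoured LTOWB; with a 2-unit saving the direction against LTOWB returned. This objection stands, and the direction has to be conditional.

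Three others stand in part.
- Section 11 does not name question 4 and sets no rule for concluding that benefit is restricted. The link is inferred from the shared threshold and term, and the harm requires someone to read the split that way.
- The target is mine, and recovery compares means while section 11 plans medians and nonparametric tests.
- Significance in one stratum only is partly low power. It occurs in 41-96% of trials when the saving is spread over 24 hours, but also in 2-64% when the saving comes only after 4 hours and there is no bias. Recovery, not the significance count, measures the bias.

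None of this makes the split a valid answer to question 4. If the direction cannot be known in advance, it cannot be allowed for when the results are read.

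**Conclusion.** The point holds in conditional form. If LTOWB moves patients across 6 units in the first 4 hours, the within-stratum comparisons are biased for the stated target. Under a roughly uniform, rank-preserving early saving, both are biased against LTOWB and a uniform benefit can look confined to either stratum. Under other shapes, or if early deaths are averted, the direction can differ or reverse. If 4-hour units are unchanged, or nobody crosses the cut, there is no bias; section 13 itself says reduced transfusion has not been shown consistently.

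All sizes rest on assumed distributions, effect shapes and 4-hour shares. They show that the distortion can be as large as the effect, not how large it will be here.

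A reader might also infer that the primary result is compromised because the grouping variable is part of the primary outcome. It is not: the overall comparison does not condition on the 4-hour count. The point should be fixed because this appears to be the only analysis of a named study question and the change is small.

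**What to change.** 1. In section 11, label the split on received units as descriptive only, and state that it will not be used to conclude that benefit is restricted to, or absent from, massive transfusion.
2. Report reaching 6 or more PRBC equivalents within 4 hours as an outcome by arm. This uses the same data as a randomised comparison.
3. To make item 2 computable, state that equivalents count on both sides of the cut (section 11 says so only for the lower group, presumably meaning both) and add a 4-hour unit count to REDCap. For patients already treated, charted times may be retrievable through the master list described in section 10.

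The cost is a few sentences and one field. The downside is that question 4 is no longer answered by this split, and the protocol should say so.

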10. LABELING & STORAGE OF DATA & SPECIMENS

No data to be stored in hard copy form. Data will be entered into secure REDCAP database, with a master list correlating study ID number, MRN, and treatment arm to be kept on LLUMC secure server.

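### The massive-transfusion split counts whole-blood equivalents in one limb only, and the data form lacks the 4-hour unit count that the split needs

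*Combined protocol and SAP*

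**What the plan says.** Section 11 of the combined protocol and SAP plans a sub-analysis of patients given "less than 6 units PRBC or equivalent in the first 4 hours or 6 units and more PRBC in the first 4 hours", the second group being labelled massive transfusion. The question it serves is the fourth in the list that closes section 8.f: whether any benefit is "restricted only to patients receiving massive transfusion (6 units PRBC or more) or in all patients receiving emergency transfusion". That question gives no time window and does not mention equivalents.

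Elsewhere the plan works in equivalents. Section 8.a counts one whole-blood unit as one PRBC plus one FFP. The first objective in section 8.b reads "Evaluate PRBC equivalents transfused in each group in the first 24 hours (Primary outcome"). The sample-size paragraph in section 6 puts both arms on one scale: "median transfusion in the component therapy group was 6 PRBC in the first 24 hours and 4 PRBC equivalents in the whole blood group".

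Whole blood is the first product in one arm only. Section 8.c gives "LTOWB: Cooler containing 2 or 4 units of LTOWB dispatched to trauma bay depending on supply"; the component (CT) cooler holds PRBC and FFP.

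The form in section 9 collects units by place of care: before arrival, in the emergency department (ED), in the hemorrhage control environment (HCE), and on the ICU or floor. A typical field is "LLUMC HCE WB (# units"). The only time limit on a unit count is in the last block: "LLUMC ICU/Floor Transfusion within first 24 hours (not including blood given prior to LLUMC, in LLUMC ED, and in LLUMC HCE").

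**The concern.** A split at 6 units needs one counting rule for both arms and a count over the stated window. The text is uncertain on the first and the form does not supply the second.

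On the counting rule, the mismatch touches only the arm that receives whole blood. A CT man given no whole blood has the same count either way. For an LTOWB man the two counts differ by the number of whole-blood units he received. An analyst who followed the wording exactly would leave some LTOWB men out of both groups and admit others to the upper group only at a higher total than CT men.

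On the count, a man can receive units in the ED, the operating room and the ICU on both sides of hour 4. Location totals do not show how many came before it.

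At stake is the planned subgroup analysis for study question 4. If the rule and the count are settled only at analysis, the grouping depends on choices that could be made after the outcomes are known.

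**Working it through.** The plan states no figure for this split, so there is none to reproduce. The check has four parts.

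**1. The rule as written.** Let W be whole-blood units and P be PRBC units in the first 4 hours. Equivalents are W + P (section 8.a).

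- Lower group: W + P < 6.
- Upper group, literal wording: P ≥ 6, that is, W + P ≥ 6 + W.
- Neither group: W + P ≥ 6 and P < 6.

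| Whole-blood units W | Upper group starts at (equivalents) | In neither group (equivalents) |
|---|---|---|
| 0 (CT) | 6 | none |
| 2 | 8 | 6–7 |
| 4 | 10 | 6–9 |

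The values 2 and 4 are the two cooler sizes in section 8.c. A man given whole blood only has P = 0 and can never enter the upper group. With equivalents in both limbs, the upper group is W + P ≥ 6, every man falls in exactly one group, and both arms are cut at 6.

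**2. The form.** The section 9 list has no 4-hour total, no transfusion times, and no times of leaving the ED or HCE. Let T be the recorded W + P from arrival.

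- If T < 6, the 4-hour count is also below 6, so the man is in the lower group for certain.
- If T ≥ 6, the 4-hour count may be anything up to T, so the form does not settle his group. Even 6 units recorded in the ED would settle it only if he left the ED before hour 4, and that time is not listed.

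**3. How many men have T ≥ 6.** This needs an assumed distribution. I take a negative binomial with SD 4 (section 6), truncated at 1 or more because every patient is transfused, with the mean set so that the median matches the planned value.

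- CT, median 6 (nominal means 6.5 to 7): P(T ≥ 6) = 54.7% to 60.3%.
- LTOWB, median 4 (nominal means 4 to 5): P(T ≥ 6) = 31.4% to 39.2%.
- With 100 per arm: 54.7 + 31.4 = 86.1, up to 60.3 + 39.2 = 99.5. That is about 86 to 99 of 200.

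The section 6 medians and SD are 24-hour figures, which suits a total count. The remaining men need no look-up.

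**4. Whether a common cut makes the arms comparable.** Suppose whole blood saves every man the planned 6 − 4 = 2 units. A man who would have used 6 or 7 units on CT then uses 4 or 5 on LTOWB and falls in the lower group. The LTOWB upper group holds only men who would have used 6 + 2 = 8 or more on CT, while the CT upper group starts at 6. The two upper groups differ in severity although the cut is the same. The shares in part 3 show the same imbalance: 55–60% of CT men against 31–39% of LTOWB men reach 6.

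**The case against.** The strongest reply is that the literal reading is not a serious one. Section 11 gives two complementary limbs in one sentence, over the same 4 hours, and ordinary usage carries the reference to equivalents across. Sections 6, 8.a and 8.b all support this, and nothing suggests that the authors meant to leave LTOWB men unclassified. This largely stands: the wording part is a clarification. It remains worth making because study question 4 repeats the omission.

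The second reply is that a field list does not rule out other sources. Section 10 provides "a master list correlating study ID number, MRN, and treatment arm to be kept on LLUMC secure server", so unit times can be sought in hospital or blood-bank records while that list exists. This also stands. Nothing is shown to be lost; the grouping variable is simply not among the planned data.

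The third reply is that a common definition does not make the comparison fair, because the grouping count is measured after assignment and treatment may change it. This is correct (part 4 of the working) and belongs in the fix.

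A reader might infer from the literal rule that the trial is set to produce a false result against whole blood in the massive-transfusion group. The documents do not support that. It requires an analyst to apply the reading that was probably not intended, and any size for the distortion needs inputs that the plan does not give: how many whole-blood units each man receives, and how mortality rises with units. For transfusion volume it would also be partly circular, since the same count would set the group and serve as the outcome. A reader might equally infer that equivalents in both limbs would remove all bias; part 4 shows that it would not.

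**Conclusion.** The point holds as a minor correction to a sub-analysis, with two defects and one missing caveat.

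- The written rule leaves LTOWB men with 6 or more equivalents and fewer than 6 PRBC in neither group. This follows from the text alone, but only on the literal reading.
- The form cannot place men with 6 or more units in total on a 4-hour split. This holds on either reading. The figure of about 86 to 99 of 200 rests on the assumed count model, the planned medians and SD, and 100 men per arm.
- Between-arm differences within a group can be biased even with a common cut, if whole blood changes the number of units given. The direction and size depend on the treatment effect, which is unknown.

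The 24-hour primary comparison is not affected, since it does not use the split.

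**What to change.** 1. In section 11 and in study question 4, define both groups on one count: whole-blood plus PRBC units given from arrival to 4 hours, below 6 versus 6 or more. Starting the count at arrival also settles that PRBC given before arrival, which the form records separately, are not included.
2. Add two fields to the section 9 form: whole-blood units and PRBC units from arrival to 4 hours, taken from blood-bank or chart times. A timed look-up is needed only for men with 6 or more units in total. It should be done before the master list is given up, since section 15 keeps that list only until data collection is complete.
3. State in section 11 that the split is made after assignment on a count that treatment may change, so that between-arm differences within a group are descriptive and may be biased even with the common cut.

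The cost is a wording change in two places, one added sentence, two fields, and a small amount of chart or blood-bank abstraction. No extra patients or procedures are needed.
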